Study Procedure	
 1) Pre-screening by clinical staff per SOP220 to identify potential subjects who would likely meet the criteria for participation in the study. 2) Recruitment Flier is provided electronically and/or hard copy is mailed out with trial Obi Gen3 Medical Robot with triadic recruitment strategy (Provider, Caregiver, Patient) 3) Screening: In-office assessment performed by provider to determine eligibility for home/community trial per Standard Operating Procedures (SOP220) that would be completed regardless of whether participating in the study. While this is not specific to the study procedure, it has been included here to help clarify the process. 4) Informed consent will be obtained for all stakeholders interested in participating (Provider, Caregiver, Patient) electronically using Qualtrics 5) ~ One (1) week home/community trial of Obi Gen 3 with a minimum of a five (5) meal requirement for use by Caregivers and

	
Patients. Providers must recommend and assess at least one (1) patient for Obi Gen 3 in their practice setting.
 
6) Following the ~ one (1) week trial, Qualtrics will send an electronic web-based link.
 
7) Participants who complete the surveys will receive a \$25 electronic gift card
 
8) Optional: Follow-up interviews completed by telephone, if warranted, within one (1) month of survey completion.

Schedule of Events	
1) Pre-Screening
 
2) Recruitment, electronic and paper flyers
 
3) Screening (In-office assessment)
 
4) Informed Consent
 
5) ~One Week Obi Gen3 trial
 
6) Survey completion
 
7) Provide \$25 remuneration
 
8) Optional follow-up interviews

A.2. Identification and description of the Investigational Device

[figure not shown]
[figure not shown]
a) Summary Description of Investigational Device

Obi is a reusable robotic utensil intended to compensate for the function of a human arm during mealtime activities to restore a person's functional eating (self-feeding) status. Obi alleviates/ameliorates the disability caused by medical diseases/conditions that completely or severely impair the upper extremities/limbs. Obi provides a cross-cultural, broad user demographic with the ability to make decisions on what and when to eat through an easy-to-learn and use user interface.

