This clinical investigation is a non-randomized, non-comparative usability study designed to evaluate whether the Obi Gen 3 Medical Robotic Feeding Device conforms to its intended use and meets documented user needs. The purpose of the study is not to assess therapeutic effectiveness or to compare outcomes across intervention groups but to validate device usability and stakeholder satisfaction across real-world settings.

Given the nature and objectives of the study, randomization, blinding, and allocation concealment are not applicable. However, several measures will be taken to minimize or avoid bias and manage potential confounding factors:

1. Standardized Protocols and Training

All participants (providers, caregivers, and patients) will engage with the device under a standardized study protocol, including consistent onboarding materials, instructional documents, and usage expectations (e.g., a minimum of five meals during the trial period). These materials were developed based on prior formative feedback and are provided in uniform formats to reduce variability in participant experience.

2. Structured Data Collection Tools

Usability feedback will be collected using validated instruments (e.g., System Usability Scale, Matching Person & Technology framework) and semi-structured interview guides. These tools ensure consistency in gathering information, reduce interviewer bias and facilitate comparisons across stakeholder groups.

3. Triangulation of Stakeholder Perspectives

The study design allows for triangulation of findings by including data from three distinct stakeholder groups (providers, caregivers, and patients). This multi-perspective approach reduces the risk of single-source bias and provides a broader understanding of device usability in real-world contexts.

4. Post-Use Feedback After Trial Exposure

Participants provide their usability ratings and feedback only after completing the one-week trial. This approach helps minimize expectation bias and ensures responses reflect the user experience with the device.

5. Blinding of Data Analysts (if applicable)

The Principal Investigator will conduct the data analysis but will not be involved directly in participant recruitment or data collection, reducing the potential for confirmation bias during the interpretation of results.

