Collectively, these measures are designed to support the credibility, reproducibility, and transparency of findings from this usability-focused clinical investigation.

c) Primary and secondary endpoints, with rationale for their selection and measurement. If applicable, composite endpoints, with rationale for their selection and measurement.

Primary Endpoint

The primary endpoint of this clinical investigation is to determine whether the production equivalent Obi Gen 3 device fulfills its intended use and formally defined user needs across three key stakeholder groups: patients, caregivers, and providers. This endpoint reflects the device's design validation objective under FDA and ISO guidelines for Class I medical devices.

To assess this endpoint, the study uses a mixed-methods approach that includes:

- Usability survey responses gathered post-trial via Qualtrics,
- Qualitative interview data to capture real-world experiences and
- Evidence of independent feeding success (i.e., completion of a minimum of five meals during the one-week trial period for patient participants).

Rationale: This endpoint aligns with ISO 13485 and FDA QSR requirements for verifying that a device conforms to documented design inputs and intended use in its target environment. Given that the device facilitates daily living activities rather than delivers clinical treatment, usability, and stakeholder satisfaction are the most relevant performance indicators.

Secondary Endpoints

Secondary endpoints are designed to provide a multi-dimensional understanding of the user experience and support future design refinement and stakeholder-specific training materials.

These include:

1. **Patient Usability** will be measured using an adapted version of the Matching Person & Technology (MPT) Framework and adult and pediatric versions. The study focuses on compatibility between the user and device, perceived benefits, and likelihood of long-term adoption.
2. **Caregiver Usability** will be measured using the System Usability Scale (SUS) and the Matching Person & Technology (MPT) Framework, an adult version adapted for the context of this study. Additionally, a few selective questions from the Caregiver Burden index will help to describe this stakeholder group to understand better the impact of Obi-Gen 3 use on time demands, emotional strain, and caregiving workload.

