- **Post-trial (~ one week to one month):** Qualtrics survey links will be sent to all participants (providers, caregivers, patients) to gather information post-trial. Optional telephone interviews may be completed within one month of survey completion for additional qualitative feedback.

Data Recording

- All survey and rating scale responses will be collected electronically via Qualtrics, a HIPAA-compliant data management platform.
- Qualitative interview notes or transcripts will be recorded and stored securely using encrypted formats, with identifiers removed before analysis.

Data Analysis: All analyses will be used to determine whether the design of Obi Gen 3 meets the intended use and user needs and to guide product refinement and support resources.

- Quantitative data will be analyzed using descriptive statistics (e.g., means, standard deviations, medians) to assess trends in usability scores across stakeholder groups.
- As a validated instrument, responses to the SUS will be interpreted using established scoring thresholds to determine whether usability targets were met.
- Qualitative data will be analyzed using a structured thematic coding approach to identify key usability themes, barriers, and suggested improvements.

e) Equipment to be used for assessing the clinical investigation variables and arrangements for monitoring maintenance and calibration.

The primary “equipment” under investigation is the Obi Gen 3 unit, which will be used by patients and caregivers in home, school, or community environments and recommended or assessed by providers in clinical settings. Each Obi Gen 3 unit used in the investigation is a production equivalent model that has

undergone quality assurance testing prior to distribution. DESIN LLC, the device sponsor, is responsible for:

- Verifying proper function of all device components (arm, base, controls) before shipment
- Maintaining a device log to track serial numbers, shipment history, and user assignment
- Providing pre-use visual inspection guidance and basic maintenance instructions to participants.

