Subjects may be withdrawn from the clinical investigation at any time due to voluntary withdrawal, investigator decision, or other unforeseen circumstances. Regardless of cause, all early terminations must be documented clearly in the Case Report Form (CRF) (attached to this protocol), including the specific reason for withdrawal. The following outlines the criteria and procedures for subject withdrawal:

Early Termination – General Considerations: All early exits from the study will be promptly recorded, and the rationale for withdrawal should be documented in the CRF to ensure traceability, transparency, and compliance with study oversight requirements.

Failure During Initial Use - While inclusion/exclusion criteria with pre-screening and in-office assessment that is part of the standard operating procedure will optimize appropriate participant selection, they may not be 100% predictive of device compatibility. In some instances, a subject may meet pre-screening criteria but be unable to use the Obi Gen 3 device safely or effectively during initial use. These cases will be identified early—typically on the first day of the trial—and such individuals will be withdrawn from the study. These withdrawals must be clearly documented in the CRF and the reason and relevant observational notes.

Voluntary Withdrawal of Consent - Subjects (or their legal representatives) have the right to withdraw consent and discontinue participation in the study at any time and for any reason, without penalty or loss of benefits. If informed consent is withdrawn, no additional data will be collected from the subject beyond the point of withdrawal. All data previously collected up to the point of withdrawal may be retained and used for analysis unless the subject explicitly requests full data removal, as outlined in the consent form.

Investigator-Initiated Withdrawal - If, at any time during the investigation, the Principal Investigator determines that continued participation poses an unforeseen risk to the subject's well-being or safety—or for other clinical, behavioral, or protocol-related reasons—the subject may be withdrawn from the study. The justification for investigator-initiated withdrawal must be documented in the CRF, and the subject (or caregiver) must be informed of the decision following ethical and regulatory standards.

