In-Office Assessment: Also part of SOP220, for screened subjects, their provider is sent a device for an in-office device assessment. During this time, the provider assesses whether the patient can use the device safely and effectively. This assessment is documented on DESIN LLC's D-FRM-021, Obi Medical Device Needs Assessment (MDNA). This form will also be filled out through Qualtrics.

Enrollment: The patients who pass pre-screening criteria per SOP220, and/or their legal authorized representative (LAR), would then be presented with the Informed Consent Form (ICF). At this time the Providers and Caregivers will also be invited to enroll in the study. Those patients who and/or their LAR sign both the ICF and study agreement, are considered enrolled in the study (Subject). Patients and/or their legal representative will be allowed ample time for review, consideration, and decision to participate in the study. A copy of the ICF should be provided to the subject and/or their LAR. After signing the ICF, the subject is assigned a sequential study number. These numbers are used for subject identification. The data platform, Qualtrics (HIPAA compliant) will be used to electronically enroll subjects.

Obi Trial: The screened subjects who pass the In-Office Assessment will take Obi home for a 7-day in home trial period in accordance with DESIN LLC's SOP220. Those subjects that complete the trial will then undergo a follow up office assessment with their provider. The providers will complete the secondary component of the MDNA form during the follow-up assessment.

Data Collection & Endpoints: Following the ~one week trial, subjects will be provided electronic links via Qualtrics to complete.

b) Description of those activities performed by sponsor representatives (excluding monitoring)

Sponsor representatives involved in this clinical investigation will engage in select study activities that support study implementation and participant engagement, while maintaining a clear separation from regulatory monitoring functions. [name], an employee of DESIN LLC (the study sponsor), will serve as a designated sponsor representative. In this role, she will perform the following non-monitoring responsibilities in direct support of the Principal Investigator, [name]:

- **Assisting with Participant Communication:** [name] will support recruitment and communication with potential and enrolled participants (providers, caregivers, and patients) throughout the study.

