Given the short duration and minimal risk nature of this usability study, the expected drop-out rate is anticipated to be low (less than 10%). Participants will be engaged for a one-week home or community-based trial of the Obi Gen 3 device,. The limited time commitment, non-invasive nature of participation, and flexibility of remote data collection (via Qualtrics and telephone interviews) are expected to support high retention.

Potential reasons for early withdrawal or loss to follow-up may include:

- Lack of interest or time to complete the trial period or follow-up activities
- Health-related issues or changes in caregiving responsibilities
- Technological issues or accessibility barriers (e.g., inability to access electronic surveys)
- In rare cases, discomfort or dissatisfaction with the device

Because the study does not involve treatment, diagnostic procedures, or invasive interventions, death is not anticipated and is not an endpoint. Any withdrawal or loss to follow-up will be documented with reason, when available. Data collected prior to withdrawal will be included in the analysis, consistent with an as-treated approach.

f) The rationale for the number of procedures to be performed by a single user as part of the learning curve and how these data are to be analysed, if applicable.

Given that this investigation evaluates the usability of a robotic feeding device designed for individuals with upper extremity impairments, caregivers, and providers, it is important to account for the initial learning period associated with device setup, operation, and integration into daily routines. The one-week trial period with a minimum expectation of five completed meals per patient/caregiver dyad is designed to reflect a realistic and sufficient exposure to allow users to become familiar with the device and overcome early learning curve effects.

This threshold was selected based on preliminary feedback from internal evaluations and stakeholder consultations, which indicated that users typically require **3–5 sessions**, to feel comfortable with basic functions (e.g., powering on, positioning the spoon, switching food compartments). For providers, the requirement to recommend and assess at least one patient supports evaluation of the device within their existing workflow, allowing observation of setup, training, and follow-up in a practical setting.

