Given the usability-focused, non-interventional design of this clinical investigation, the approach to managing missing, unused, or spurious data will prioritize transparency, traceability, and context-based interpretation rather than imputation or statistical correction.

Missing Data - All efforts will be made to minimize missing data by:

- Using structured and user-friendly electronic data collection tools (Qualtrics),
- Providing reminders for survey completion, and

- Offering support to participants during the trial period.

When data are missing, the specific nature and reason for the missing information (e.g., participant withdrawal, technical issues, non-response) will be recorded in the study database. Missing data will not be imputed, as the primary goal is descriptive analysis rather than inferential statistical modeling. Analyses will be conducted using available data only, and the extent of missingness will be reported for each data element.

Unused or Incomplete Data - Incomplete survey responses or interviews that do not meet minimal content thresholds (e.g., <50% of questions answered) may be excluded from individual item-level analysis but will be retained in the dataset for auditability. The rationale for excluding such data will be documented in the data analysis plan and in the final study report.

Spurious or Implausible Data - Any values that are clearly spurious (e.g., internal inconsistencies, out-of-range responses) will be flagged during data quality checks. If these data cannot be resolved through source verification (e.g., interview notes, metadata review), they will be excluded from analysis and annotated accordingly in the dataset with justification.

Participant Drop-outs - Participants who withdraw from the study after enrollment will be asked, if willing, to provide a brief reason for withdrawal. Drop-outs will be tracked, and their status will be clearly documented in the final dataset. Data collected prior to withdrawal will be included in the analysis unless the participant requests removal of their data per the informed consent agreement. The rate and pattern of drop-outs or early discontinuation will be described in the final study report to assess potential biases or operational challenges affecting the usability evaluation.

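### Patients withdrawn because they cannot use Obi3 are not scheduled for any usability rating, so the descriptive results lean towards the device

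*Protocol*

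**What the plan says.** Section A.6.1 b) 4 lists the timing of ratings among the measures against bias: "Participants provide their usability ratings and feedback only after completing the one-week trial". Other sections follow the same timing. The synopsis procedure says "Following the ~ one (1) week trial, Qualtrics will send an electronic web-based link". Section A.6.1 c) bases the primary endpoint partly on "Usability survey responses gathered post-trial via Qualtrics". Section A.6.4 a) adds: "Those subjects that complete the trial will then undergo a follow up office assessment with their provider".

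Section A.6.3 c) i) foresees that some screened patients will be unable to use the device safely or effectively. They are identified "typically on the first day of the trial" and withdrawn, with the reason and observational notes entered in the CRF. Under A.7 m), people who withdraw "will be asked, if willing, to provide a brief reason for withdrawal". Section A.7 e) 6) promises: "Data collected prior to withdrawal will be included in the analysis, consistent with an as-treated approach".

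Two sections use looser wording. Section A.6.1 d) says "Qualtrics survey links will be sent to all participants (providers, caregivers, patients) to gather information post-trial". Section A.6.3 c) ii) starts reminders when a survey is outstanding a week after the designated trial period, which is a calendar trigger and not a completion trigger.

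**The concern.** The protocol places the study's value in finding what helps and what hinders use (A.5 d) and in revealing design limitations (A.6.4 e). A patient who cannot operate Obi3 on the first day has met the most serious barrier of all, yet the schedule contains no occasion on which that patient rates the device. The missingness is thus caused by the outcome: failing with the device removes the rating.

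The analysis cannot repair this. A.7 m) rules out imputation, A.7 a) limits the analysis population to people who completed the survey, and the promise to use data collected before withdrawal has no post-exposure rating to work on. A.6.1 f) also lets recruitment continue after early attrition, so people who could not use the device may be followed by people who can. At stake is whether user-needs percentages, SUS and MPT summaries and qualitative themes describe everyone who tried the device or only those who managed the week.

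**Working it through.** **Who is lost.** Following each kind of participant through the stated rules:

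- *Patient withdrawn for failure at initial use.* The week is never completed, so A.6.1 b) 4 gives no rating and A.6.4 a) gives no follow-up office assessment. The interviews do not fill the gap, because they are optional and follow up survey responses (synopsis; A.6.3 c) ii). The user-needs survey and modified MPT are lost. The CRF reason, the notes and an optional brief reason remain.
- *That patient's caregiver.* The caregiver shares the same week and the same five-meal minimum, and the link follows the trial. Nothing triggers it once the patient is withdrawn. The survey, SUS and modified MPT are probably lost.
- *Provider.* The requirement is to recommend and assess at least one patient (synopsis), which one patient's withdrawal does not undo. The provider is not clearly lost.
- *Patient or caregiver who stops using the device but is not withdrawn.* A.6.1 b) 4 excludes a rating; A.6.1 d) and A.6.3 c) ii) can be read as including one. The sections conflict.

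**How much it could matter.** Inputs from the protocol: 20 per stakeholder group (A.6.3 h; 3 × 20 = 60, which reproduces the stated total), drop-out under 10% (A.7 e) 6), a user-needs threshold of 50% among completers (A.7 g), and a SUS reference value of 68 (A.5 d). Assumptions: the drop-out rate applies within each group, each early exit is unfavourable on user needs, the completers' mean caregiver SUS is 70, and each early-exit SUS is 40.

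Number of exits: 0.10 × 20 = 2, so strictly under 10% means at most 1 per group.

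| Early exits of 20 | Lowest pass among completers | Same count over all 20 | Caregiver SUS mean with exits added |
|---|---|---|---|
| 1 | 10/19 = 52.6% | 10/20 = 50% | (19 × 70 + 40)/20 = 68.5 |
| 2 | 9/18 = 50% | 9/20 = 45% | (18 × 70 + 2 × 40)/20 = 67.0 |

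With one exit, nothing crosses a threshold: 50% still meets the rule and 68.5 is still above 68. Crossing needs two exits, which is exactly 10% and so outside the stated expectation. Even then, the move from 9/18 to 9/20 is a change of denominator. A.7 g) applies its rule to people who complete the week, so collecting early-exit ratings would leave that calculation at 9/18. SUS is not among the A.7 g) criteria; A.5 d) uses 68 to put findings in context.

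**The case against.** The strongest reply has four parts.

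1. *Rating after exposure is a reasoned choice.* A.7 f) says users typically need 3–5 sessions to feel comfortable, so a scale score after one failed meal measures something different. This stands as a reason to flag such ratings, but not to omit them. Guarding against expectation bias requires use of the device, not completion of the week.
2. *The barrier is not unknown.* The CRF holds a reason and notes, A.7 m) commits to describing the rate and pattern of drop-outs, device deficiencies are reported separately, and the in-office assessment screens out unsuitable users beforehand. This stands in part: some knowledge of the barrier survives. What is missing is the structured response that every reported summary is built on.
3. *Early stoppers may be surveyed anyway.* A.6.1 d) and A.6.3 c) ii) allow that reading for people who stop without being withdrawn. It does not reach patients already withdrawn under A.6.3 c) i), and it conflicts with A.6.1 b) 4.
4. *The numbers are small.* That is correct, and it limits the point to the descriptive results.

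It might also be said that no data may be taken after withdrawal. A.6.3 c) i) bars further collection when consent is withdrawn. A patient withdrawn for inability to use the device has not necessarily withdrawn consent.

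**Conclusion.** The point holds for patients withdrawn for failure at initial use and, probably, for their caregivers: the protocol as written obtains no user-needs, SUS or MPT response from them. Because failure with the device is what removes the rating, the descriptive results and themes for patients and caregivers are biased in the device's favour. The expected loss is at most 1 of 20 per group if the drop-out figure holds and applies evenly across groups. The reasons for drop-out listed in A.7 e) 6) do not name inability to use the device, so that figure may not cover first-day failures.

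A reader might infer more: that nobody who stops early ever gives a rating, that all three groups are affected alike, or that the omission could turn a fail into a pass. The documents do not support these. Early stoppers who are not withdrawn may be surveyed under the looser sections, providers are not clearly lost, and no pass/fail change is shown at the stated drop-out. The A.7 g) rule rests on completers and stays there unless it is edited separately.

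**What to change.** In A.6.1 b) 4, A.6.1 d) and the Schedule of Events, have ratings collected *at completion of the trial or at early discontinuation of device use, whichever comes first*, and bring A.6.3 c) ii) into line. On early discontinuation, send the existing Qualtrics link to the patient and the caregiver unless that person has withdrawn consent, and state that the provider is surveyed regardless. Flag early-exit responses as brief-exposure ratings, and report user needs, SUS, MPT and themes with and without them.

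The cost is a changed survey trigger, some protocol wording and a few more $25 gift cards. The small downside is that these ratings reflect use short of the 3–5 sessions in A.7 f), which the flag and the two-way reporting make visible. No withdrawal or device-use rule changes. The edit should be made before enrolment, because ratings not taken at the time cannot be recovered later.
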